ClinicalTrials.gov Data Entry Cover Sheet

Protocol ID: 22811 **Clinical Trials.gov ID:** NCT05988398

Project Title: Preventing Commercial Sexual Exploitation of Children (Project LIVE)

Principal Investigator: [name], University of Nebraska-Lincoln

Statistical Design and Power

Power Analyses

Aim 1a. N/A

Aim 1b. There is no “magic bullet” for sample size in qualitative research.¹²⁷⁻¹²⁹ The sample size proposed for focus groups is consistent with other research conducted by the PI and Co-I ([name]) that should allow for saturation (i.e., the collection of new data does not produce additional insights).¹³⁰ However, the sample size may be adjusted until data saturation is achieved.¹³⁰

Aim 1c. N/A

Aim 1d. Power analyses to support the sample size for the measurement development study (for multi-item measures) are based on prior simulation work.¹³¹ The proposed sample size of $n=878$ baseline surveys from youth will be utilized by splitting the sample in half to conduct exploratory factor analysis (EFA) and confirmatory factor analysis (CFA), each with 439 youth. A sample size of 439 youth is adequate for implementing factor analyses using structural equation modeling approaches and provides power ($> .80$) to estimate two factor models, five manifest indicators each, nonnormal data, and factor loadings = .80.

Aim 1e. Regarding qualitative data, see narrative above for Aim 1b. Also, power analyses were not conducted for descriptive data (e.g., frequencies of the number of sessions attended, extent to which sessions were delivered with fidelity). Regarding student survey data collected as part of the OPT, we will examine changes in intermediary outcomes (see Figure 1) over time given that there will likely not be a sufficient window of time to see changes in behavioral primary and secondary outcomes at the immediate post-test which will happen within a few days to a week or two following the ending of the programming. For the exploratory program impact analysis on intermediary outcomes (Figure 1), a sample size of $n=878$ (approximately .5 assignment rate to condition), will provide adequate power (.80; $\alpha=.05$) to detect a minimum effect size (MDES) $d=.20$ as determined by G-Power analysis of covariance (ANCOVA) routine.

Aim 1f. N/A

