Aim 2a. Power analyses to support the sample size for the effectiveness analyses for our primary, secondary, and intermediary outcomes (see Figure 1) were conducted using G-Power 3.1. Power was set to .80 and $\alpha=.05$. Component A of the study will provide incidence rates which will be used to recalculate power prior to the implementation of Component B. For the purposes of this proposal, we calculated the MDES based on the proposed sample size. For the primary outcome of CSEC perpetration, there are no reliable incidence estimates in the literature on which to draw. With a sample size of 7,241 students enrolled, assuming conservative minimum incidence rates of CSEC perpetration of 1% to 5% (although we hypothesize it will be higher), we have power to detect an MDES difference between conditions, odds ratio (OR)=.49 to .75, respectively. Similarly, for secondary outcomes of CSEC victimization, we estimated a range of incidence rates from a conservation 5% to 50%+ based on literature discussed following for other types of victimization^{96, 132, 133} as well as rates of CSEC youth at increased risk (e.g., system involved, homeless)¹⁸⁻²⁰, which will be present in our sample based on DMPS data, we have the power to detect an MDES difference between conditions, odds ratio (OR)=.75 to .88, respectively. For secondary outcomes of TDV/SV perpetration and victimization, given past 12- months incidence rates¹³² (from nationally representative data from youth) of 63% for perpetration (of any type of TDV) and 69% for victimization (of any type of TDV), we have power to detect an MDES difference between conditions, odds ratio (OR)=.88 to .89. For sub-types of TDV (past 12-month incidence rates: physical victimization: 18%; sexual victimization: 18%; psychological victimization: 66%; physical perpetration: 12%; sexual perpetration: 12%; psychological perpetration: 62%)¹³², we have power to detect an MDES difference between conditions, odds ratio (OR)=.83 to .89, respectively. For the secondary outcome CSEC bystander action and opportunity and intermediary outcomes (i.e., knowledge, valuing of self and others, healthy relationship skills, bystander efficacy, perceptions of school social norms, prevention conversations with school personnel), the ANCOVA routine suggested power (.80) to detect a small difference between groups (MDES $d=.06$).

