
propensity score. For categorical variables, logistic regression will be used to examine differences in prevalence by condition. The experimental condition is the independent variable in these models. Multilevel modeling is not possible given the small number of schools; thus, school will be included as a covariate. Classroom will be used as a cluster variable to adjust the standard errors for nesting. Models for Step 4 will be evaluated for overall model fit via χ^2 statistic, RMSEA :s .08, SRMR :s .10, and CFI \geq .90. We will evaluate our hypotheses across several indicators, including significance (p), confidence intervals, and the standardized difference between groups (d), as well as the directionality of included path coefficients, and odds ratios.

Mediation and Moderation Analyses (Aim 2b).

We will assess mediators (e.g., perceptions of norms intolerant of CSEC) and demographic moderators (e.g., gender) of program effectiveness, including the propensity score and school as covariates in all models. To test for mediation, we used the product of coefficients method using bias-corrected bootstrapping with 1000 resamples to calculate the confidence intervals¹⁴⁵ (MacKinnon, 2012). For our moderators (e.g., age, gender, racial groups, sexual orientation), we will estimate structural equation multiple group models, first allowing estimation of the path coefficients to vary freely across groups, and then constraining paths to be equal when a structural path coefficient of interest was significant for one group and not the other group. We will conduct model comparisons using the chi-square (χ^2) difference test (i.e., χ^2 , $p < .05$ indicating moderation).

Aim 2c. Descriptive statistics will be used to examine the extent to which sessions were delivered with fidelity. Process observations will be analyzed using thematic analysis as described above for Aim 1b.

Aim 2d. Descriptive statistics will be used to examine the frequency of responses to close-ended questions (e.g., To what extend did you like the session today?). Open-ended questions will be analyzed using thematic analysis as described above for Aim 1b.

Aim 2e. Interview data will be analyzed using thematic analysis as described above for Aim 1b.

Aim 2f. The purpose of this aim is to determine costs associated with the program implementation to inform future economic evaluation of the RTS. The process for documenting costs are described in Section C.18.

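### The Aim 2a power figures, above all the detectable odds ratios for the primary outcome, treat 7,241 students as independent and make no allowance for the classroom clustering in the planned analysis

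*SAP*

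**What the plan says.** In the SAP, Power Analyses, Aim 2a, the calculations for primary, secondary and intermediary outcomes "were conducted using G-Power 3.1", with power .80 and alpha .05. The input is the 7,241 students enrolled. At 1% to 5% incidence of CSEC perpetration, the primary outcome, the conclusion is "we have power to detect an MDES difference between conditions, odds ratio (OR)=.49 to .75, respectively". For bystander action and the intermediary outcomes, "the ANCOVA routine suggested power (.80) to detect a small difference between groups", given as d=.06. Aim 1e uses 878 students and states d=.20, "as determined by G-Power analysis of covariance (ANCOVA) routine".

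Nowhere do the Power Analyses mention an ICC, a class size, a number of classrooms, a design effect or an effective sample size.

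The Proposed Analyses for Aim 1e and for Aim 2a both state: "Classroom will be used as a cluster variable to adjust the standard errors for nesting". Aim 2a also weights students by inverse probability of condition and enters school as a covariate. The SAP plans to recalculate power before Component B, using incidence rates from Component A.

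**The concern.** The SAP powers one analysis and plans another. Students in the same classroom tend to resemble each other. If a classroom shares a condition, a cluster-adjusted standard error for the condition effect will usually be larger than one that treats students as independent. A power figure without that allowance is too favourable.

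The primary outcome has most at stake. It is assumed to be rare, so the detectable odds ratio is already far from 1 at the lower incidence. If the trial finds no significant difference, readers will use the stated odds ratios to judge what size of effect it could have found. The planned recalculation would carry the gap forward, because it updates incidence and nothing else.

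**Working it through.** **Inputs from the SAP.** N=7,241 (Aim 2a) and 878 (Aim 1e); alpha .05; power .80; incidence 1% and 5%. Allocation is about 1:1 for Aim 1e, and I assume the same for Aim 2a, so n=3,620.5 per arm. Sidedness is not stated. The normal quantiles are 1.645 (one-sided), 1.960 (two-sided) and 0.842 (80% power); one-sided, 1.645+0.842=2.486 before rounding.

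**Step 1: reproduce the odds ratios with independent students.** Convert the OR to a comparison proportion, p2 = o/(1+o) with o = OR × p1/(1−p1). Then R = (p1−p2)/√{[p1(1−p1)+p2(1−p2)]/n}, and one-sided power is Φ(R−1.645).

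- p1=.01, OR .49: p2=.00493, R=.005075/.002022=2.51, power Φ(0.865)=81%.
- p1=.05, OR .75: p2=.03797, R=.012025/.004818=2.496, power Φ(0.851)=80%.

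Solving for 80% power gives OR .494 at 1% and .751 at 5%, against the stated .49 and .75. The largest design effect that keeps 80% power is (R/2.486)², which is about 1.02 at 1% and 1.01 at 5%. The primary-outcome figures therefore leave no room for clustering.

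**Step 2: reproduce d.** MDES = 2.486 × 2/√7,241 = .058 one-sided, against the stated .06. Power at d=.06 is 82%, and 80% is kept up to a design effect of (.06/.0584)²=1.05. Because of rounding, d=.06 identifies the design effect less sharply than the odds ratios do: any value up to about 1.23 would still print as .06.

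**Step 3: two-sided.** With independent students, power is 71% at OR .49, 70% at OR .75 and 72% at d=.06.

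**Step 4: add clustering.** Three assumptions are needed, none of them from the documents: m=25 students per class, whole classrooms sharing a condition, and an ICC of .01, .02 or .05. School is a covariate, so the relevant ICC is the residual one within school. DEFF = 1+(m−1)×ICC = 1+24×ICC, effective N = 7,241/DEFF, and R is divided by √DEFF.

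| ICC | DEFF | Effective N | Power at OR .49 (1%) | Power at OR .75 (5%) | Detectable OR, 1% | Detectable OR, 5% | Power at d=.06 |
|---|---|---|---|---|---|---|---|
| .01 | 1.24 | 5,840 | 73% | 72% | .45 | .73 | 74% |
| .02 | 1.48 | 4,893 | 66% | 66% | .40 | .70 | 68% |
| .05 | 2.20 | 3,291 | 52% | 52% | .30 | .64 | 53% |

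All entries are one-sided. Example: at OR .75 and DEFF 1.48, R=2.496/1.217=2.052 and power is Φ(0.407)=66%. Two-sided power at OR .75 is 61%, 54% and 39%. The d column is before any gain from baseline adjustment. The loss from IPTW is not included, because nothing in the documents allows it to be sized.

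**Step 5: Aim 1e.** With 878 independent students the MDES is 2.802×2/√878=.189 two-sided and .168 one-sided. The stated d=.20 therefore holds up to a design effect of (.20/.189)²=1.12 two-sided or (.20/.168)²=1.42 one-sided. At 25 per class these are ICCs of about .005 and .018.

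**The case against.** Four arguments on the other side carry weight.

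- **Baseline adjustment.** If d is on the raw outcome scale, a covariate with R² = 1−1/DEFF cancels the clustering loss: .19 at DEFF 1.24 and .32 at 1.48, or pre-post correlations of about .44 and .57. Such values could occur for continuous outcomes, so their loss may be partly or wholly recovered. But the SAP states no R², and for Aim 2a it names the propensity score and school as covariates. The argument is unlikely to help a binary outcome at 1% to 5%.
- **Assumed inputs.** The size of the loss rests on an ICC, a class size and a unit of assignment that the documents do not give. If conditions are mixed within classrooms, the design effect is smaller. This limits how firmly the size can be stated, but the omission itself is not in doubt.
- **Provisional figures.** The SAP presents the Aim 2a figures as calculated for the proposal and promises a recalculation. That recalculation covers incidence rates only.
- **Other ways of judging results.** The SAP also uses confidence intervals and standardized differences, so a non-significant result need not be read as excluding an effect. That softens the consequence, but the power statement still needs correcting.

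A reader might infer that every detectable effect in the SAP is wrong, or that all of them reproduce only with a design effect of exactly 1. The documents do not support that. The d figures are compatible with a modest design effect, Aim 1e has slack, and the Aim 2b results rest on simulation work whose treatment of clustering is not described.

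**Conclusion.** The point holds for Aim 2a, and most firmly for the primary outcome. The stated odds ratios of .49 and .75 correspond to about 80% power only for independent students at one-sided alpha .05, while the planned model adjusts for classroom. With 25 students per class sharing a condition and a within-school ICC of .01 to .05, one-sided power at those odds ratios is about 73% down to 52%. The detectable OR moves to .73–.64 at 5% incidence and to .45–.30 at 1%.

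For d=.06 the same assumptions give 74% down to 53% before baseline adjustment, so the net loss for continuous outcomes remains open. Sidedness is a separate gap: if the tests are two-sided, these Aim 2a figures give only about 70–72% power before any clustering.

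Aim 1e has the same omission, but it is exploratory and its d=.20 may still hold. The Aim 2b simulation-based figures are not shown to be affected. Nor do the documents show that the study needs more students: they show that its stated sensitivity rests on an allowance that was left out.

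**What to change.** 1. In the Power Analyses, state whether tests are one- or two-sided, the unit of assignment, the expected class size and a range for the classroom ICC within school.
2. Restate the Aim 2a odds ratios and d, and the Aim 1e d, on the effective sample size N/[1+(m−1)ICC]. Under the assumptions above with ICC .02, one-sided, this gives about OR .70 at 5% incidence, OR .40 at 1%, and d=.07 for N=7,241. For n=878 it gives d=.20 one-sided or .23 two-sided.
3. Add an explicit allowance for IPTW weighting. State any baseline R² that is relied on, and for which outcomes.
4. Extend the recalculation planned before Component B to include the classroom ICC estimated from the Component A surveys, alongside the incidence rates.
5. For Aim 2b, say whether the simulations included classroom clustering.

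The cost is SAP wording and a short recalculation, with no extra students. The drawback is that the published figures become less favourable.

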Aim 2b. For the mediation analyses, based on simulation literature^{134, 135}, a sample size of 7,241 provides power ($> .80$) to detect small effects ($a=.28$; $b=.14$), which are typical of mediation designs. For the moderation analyses, we used simulation-based approach to power analysis using Mplus¹³¹. We used a multiple group model, assuming categorical moderators (e.g., gender). The proposed sample size provides sufficient power ($> .80$) to detect moderation group differences in treatment effects, $b=.20$. As an alternative way to examine power for moderation of treatment effects, we examined the MDES within moderation groups. For this analysis (G-Power ANCOVA), we took a conservative approach and used the moderator that may have the largest discrepancy in group size, such as gender identity and sexual orientation. Based on population data, we estimate 2.5% will identify as a gender minority (inclusively defined, e.g., trans, non-binary, gender queer, Two Spirit)¹³⁶⁻¹³⁸, leaving a sample size of $n=181$; and 10% of the sample will identify as a sexual minority^{113, 139}, leaving a sample size of $n=724$. Simulation power analysis supports being able to detect a small condition group difference, MDES $d=.20$.

Aim 2c. N/A

Aim 2d. N/A

Aim 2f. N/A

Proposed Analyses

Aim 1a. N/A

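### The stated power of .80 to detect moderation at b=.20 is not supported for the 2.5% gender-minority group (about 26% if b is in SD units), is borderline for the 10% sexual-minority group, and does not describe the conditional test that is planned.

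*SAP*

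**What the plan says.** SAP, Power Analyses, Aim 2b, gives two supports for moderation power.

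- The first is an Mplus simulation: "We used a multiple group model, assuming categorical moderators (e.g., gender"). Its conclusion is: "The proposed sample size provides sufficient power ($> .80$) to detect moderation group differences in treatment effects, $b=.20". The group sizes, the outcome SD and the scale of b are not given.
- The second begins: "As an alternative way to examine power for moderation of treatment effects, we examined the MDES within moderation groups". It takes the moderators with the most uneven groups. Gender minority is put at 2.5% of the sample, "leaving a sample size of $n=181", and sexual minority at 10%, or 724. One figure, d=.20, is then given for both. The SAP attributes this analysis first to the G-Power ANCOVA routine and then to simulation.

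SAP, Proposed Analyses, Mediation and Moderation Analyses (Aim 2b), sets the decision rule: "We will conduct model comparisons using the chi-square" difference test, with p < .05 taken as moderation. Paths are first left free across groups. They are constrained to equality only where the path of interest reaches significance in one group and fails to in the other.

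**The concern.** Moderation is a statement about the difference between two treatment effects, and the variance of that difference is dominated by the smaller group. A power of .80 at b=.20 may be right for evenly split groups and wrong for a 2.5% group. The SAP does not say which split its simulation used. The figure it offers for the small groups is the effect detectable inside one group, and the same value is printed for sizes that differ fourfold (724/181 = 4).

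At stake is the interpretation of Aim 2b. A reader who relies on the stated power could take a non-significant moderation test for gender identity as informative when it is not.

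**Working it through.** **Inputs from the SAP.** Total: "With a sample size of 7,241 students enrolled" (Power Analyses, Aim 2a). Error rates: "Power was set to .80 and $\alpha=.05" (Aim 2a; carried over to Aim 2b). Groups: 181 vs 7,241 − 181 = 7,060, and 724 vs 7,241 − 724 = 6,517.

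**Assumptions.** Continuous outcome with SD 1; two-sided test; 1:1 arms in every group (the SAP gives a rate of about .5 only for the pilot, Aim 1e); no covariate gain and no clustering at first. The SAP gives no R-squared, ICC or design effect for Component B.

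**Step 1: the SAP's own within-group figure.** SE = 2/√n; detectable d at 80% = (1.96 + 0.84) × SE.
- n=724: SE .0743, detectable .208 (.209 with the ANCOVA routine); power at .20 is 77%.
- n=181: SE .1487, detectable .416 (.419 with the ANCOVA routine); power at .20 is 27%.

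So .20 is close for 724 and too small by a factor of about two for 181. To reach .20 with 181 students, covariates would have to explain about 77% of the outcome variance.

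**Step 2: the between-group test.** SE = 2√(1/n1 + 1/n2); power = Φ(.20/SE − 1.96).
- 724 vs 6,517: SE .0783, z = 2.55, power 72%, detectable .220. A 20,000-replicate simulation gave 72.8%.
- 181 vs 7,060: SE .1506, z = 1.33, power 26%, detectable .422. Simulation gave 26.1%.
- Equal halves, for comparison: SE .0470, z = 4.25, power 99%, detectable .132.

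Going from the within-group to the between-group basis costs about 4 points for 724 (77% to 72%) and under 1 point for 181 (26.8% to 26.4%).

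**Step 3: range over what the SAP leaves open.** SE is multiplied by √[(1 − R²) × design effect].

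| Setting | 724 vs 6,517 | 181 vs 7,060 |
|---|---|---|
| Base | 72% | 26% |
| R² .25 | 84% | 34% |
| R² .50 | 95% | 47% |
| Design effect 1.2 | 64% | 23% |
| Design effect 1.5 | 55% | 19% |
| R² .25 and design effect 1.5 | 67% | 24% |
| b is a standardized path | >99% | 77% |

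In the last row, d = 2b/√(1 − b²) = .40/√.96 = .41. Without clustering, 80% needs R² of about .17 for sexual orientation and .78 for gender identity.

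**Step 4: the precondition.** I simulated the full procedure under the base assumptions. The true difference is .20 in every row (minority effect first; for equal halves, one half vs the other).

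| Effects | 724 vs 6,517 | 181 vs 7,060 | Equal halves |
|---|---|---|---|
| .20 vs 0 | 67% | 24% | 94% |
| 0 vs .20 | 70% | 24% | 94% |
| .30 vs .10 | 2% | 0.6% | 15% |

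The collapse in the last row is easy to see for 724 vs 6,517. The majority effect of .10 has SE 2/√6,517 = .0248, so z = 4.04 and it is almost always significant. The test is then run only if the minority estimate is non-significant, that is, within ±1.96 × .0743 = ±.146. Rejection needs a gap above 1.96 × .0783 = .154. With the majority estimate near .10, a minority estimate below .146 can meet that only by falling under about −.05, opposite in sign to the true effect.

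**The case against.** The strongest reply is that the SAP does address the right quantity. Its first support is a simulation of the between-group difference, and the within-group figure is offered only as an alternative. This stands. A reader might infer that moderation power rests on a within-group effect size alone; the text does not support that. The gap is that the simulation's group sizes and the scale of b are missing. Its only named example is gender, so it cannot be assumed to cover a 10% or 2.5% group.

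A reader might also infer that the within-group basis causes the shortfall. Step 2 shows otherwise: the small group dominates both variances, and the two detectable effects nearly coincide (.21 and .22; .42 and .42).

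Nor do the documents support calling sexual orientation underpowered outright. Modest covariate gain lifts it above 80% and modest clustering lowers it, and the SAP quantifies neither.

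Finally, the SAP does not say that a non-significant test will be read as equal effectiveness. That is a risk, not a stated plan. Moderation is also part of Aim 2b, and the primary effectiveness test does not depend on it.

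**Conclusion.** The point holds in a limited form. For gender identity the claim of more than .80 at .20 fails if b is in SD units: about 26% under simple assumptions, and 19% to 47% over the R-squared and design-effect values examined. If b is a standardized path, power is about 77%, so even then the claim is only approached. Sexual orientation is borderline at about 72%, with 84% at R-squared .25 and 55% at design effect 1.5. The main numerical error is one d=.20 for both subgroups, when 181 students give about .42 on either basis.

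Separately, none of these figures describes the procedure as written. The significance precondition makes power depend on the pattern of effects, and even equal halves fall to about 15% at .30 vs .10. The exact percentages rest on SD 1, 1:1 arms and two-sided .05, none of which the SAP states for this analysis. The gender-identity shortfall at a .20 SD difference is robust to the covariate gain and clustering examined.

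**What to change.** In Power Analyses, Aim 2b:
- For each named moderator, state the detectable between-group difference with its group sizes, the scale of b, and the assumed R-squared and design effect. Before covariates and clustering this is about .22 for sexual orientation and .42 for gender identity.
- State the group sizes used in the b=.20 simulation, and limit the .80 claim to the splits it covers.
- Keep the within-group MDES only as the precision of subgroup effects, with separate values of about .21 (n=724) and .42 (n=181).

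In Mediation and Moderation Analyses (Aim 2b):
- Run the chi-square difference test for every pre-specified moderator path, without the condition that one group's path be significant and the other's not. Otherwise the restated power does not apply.
- Report the difference in effects with its confidence interval, and say that non-significance in the small groups will not be read as absence of moderation.

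The cost is SAP wording and a short recalculation, which fits the power update already planned before Component B. The stated moderation power becomes less favourable, and more moderation tests will be run.

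### Aim 2b gives one within-group MDES, d = .20, for subgroups of 181 and 724; it is about right for 724, but 181 gives about .36 to .42

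*SAP*

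**What the plan says.** SAP, Power Analyses, Aim 2b, first reports a simulation in Mplus for differences in treatment effect between moderator groups. It then offers a second view of power, in which "we examined the MDES within moderation groups". The method and its intent are stated: "For this analysis (G-Power ANCOVA), we took a conservative approach and used the moderator that may have the largest discrepancy in group size".

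Two groups follow, both taken as fractions of the 7,241 students. Gender-minority students are put at 2.5%, "leaving a sample size of $n=181", and sexual-minority students at 10%, "leaving a sample size of $n=724". The paragraph ends with one result: "Simulation power analysis supports being able to detect a small condition group difference, MDES $d=.20". Nothing assigns that value to one group or the other. Sidedness, allocation and covariate correlation are not given for this calculation.

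The SAP reports the same ANCOVA routine in two other places:

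- Aim 1e, n=878: power "to detect a minimum effect size (MDES) $d=.20$ as determined by G-Power analysis of covariance (ANCOVA) routine".
- Aim 2a, n=7,241: "the ANCOVA routine suggested power (.80) to detect a small difference between groups (MDES $d=.06".

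**The concern.** At fixed power and alpha, the MDES is proportional to 1/√n. A fourfold difference in n means about a twofold difference in MDES, whatever common choice is made for covariates, sidedness or allocation. A single d therefore cannot be the MDES for both groups. It is also odd that d=.20 is reported for 878 students in Aim 1e and again in a paragraph whose smallest group has 181.

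The figure is presented as the conservative check, and it is the only MDES the SAP gives within small subgroups. If .20 is taken to cover gender-minority students, a null result in that group could be read as evidence against a small effect, when the study would miss a true d=.20 about two times in three or more.

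The paragraph is also inconsistent about method: it names G-Power ANCOVA for this analysis and then credits the result to simulation.

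**Working it through.** **Inputs**

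- Subgroup sizes (SAP, Aim 2b): 2.5% × 7,241 = 181 and 10% × 7,241 = 724. Both agree with the SAP.
- Power .80 and alpha .05: stated for Aim 2a and carried over.
- Two-sided test: assumed. The 1-df ANCOVA F test is two-sided.
- Allocation 1:1: assumed. The SAP states about .5 for the pilot (Aim 1e) only.
- Covariate-outcome correlation ρ: not stated, so shown as a range.
- Students treated as independent.

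**Formula**

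ANCOVA F test with one covariate: df1 = 1, df2 = n − 3, noncentrality λ = n·d² / [4(1 − ρ²)]. The MDES is the d that gives power .80. As a hand check, d ≈ 2(1.960 + 0.842)·√(1 − ρ²) / √n.

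**Step 1. Does the method reproduce the SAP's other ANCOVA figures?**

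- n=878, ρ=0: d=.189 (SAP: .20).
- n=7,241, ρ=0: d=.066; at ρ=.41, d=.060 (SAP: .06).

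The method and the d scale match the SAP's approximately.

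**Step 2. MDES in the two subgroups**

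| n | ρ=0 | ρ=.3 | ρ=.5 |
|---|---|---|---|
| 724 | .209 | .199 | .181 |
| 181 | .419 | .400 | .363 |

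Hand check at ρ=0: 5.60/√724 = .208 and 5.60/√181 = .416. For n=724, d reaches .200 at ρ=.28.

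**Step 3. Power at d=.20**

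| n | ρ=0 | ρ=.3 | ρ=.5 |
|---|---|---|---|
| 724 | 77% | 80% | 87% |
| 181 | 27% | 29% | 34% |

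**Step 4. Scaling the SAP's own figures by 1/√n**

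- From .06 at 7,241: .06 × √(7,241/181) = .38 at n=181 (.35 to .41 if .06 is rounded from .055 to .065); .06 × √(7,241/724) = .19 at n=724.
- From .20 at 878: .20 × √(878/181) = .44 at n=181; .20 × √(878/724) = .22 at n=724.

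Both put .20 near n=724 and far from n=181.

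**Step 5. What would make .20 true at n=181?**

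- A covariate correlation of about .88: .4187 × √(1 − .88²) = .199. The same correlation would give .031 at 7,241 (SAP: .06) and .09 at 878 (SAP: .20).
- A one-sided .05 test with ρ=0 still gives .371.
- Unequal allocation makes it worse: .427 at 40:60 and .484 at 25:75, with ρ=0.

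**The case against.** The strongest objection is that the SAP never says .20 applies to n=181. The larger group is the nearest antecedent, so the sentence may be incomplete rather than false. That ambiguity is real. But the SAP says it chose the moderator with the largest discrepancy in group size in order to be conservative, and that description fits 2.5% better than 10%. If .20 was meant only for n=724, the conservative check omits the smallest group named, and the same edit is needed.

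Other points stand in part:

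- **The fit at n=724 is approximate.** With no covariate gain the MDES is .209, power at .20 is 77%, and 80% needs 787 students. The .20 should carry its covariate assumption.
- **The figure could be a Cohen's f labelled d.** Since f = d/2, the f for n=181 is .209, as close to .20 as the d for n=724. The documents cannot settle this. The d for n=181 would still be about .42.
- **The range .36 to .42 depends on stopping at ρ=.5.** At ρ=.7, n=181 gives .30: lower, but still 1.5 times the stated value.
- **The two calibration figures imply different inputs.** The .06 needs ρ near .41, while .20 at 878 is looser than ρ=0. They are rough evidence, but neither supports .20 at n=181.
- **Clustering matters little at n=181.** Assume classes of 20 to 30, intraclass correlation .05 to .10, and a design effect of 1 + (class size − 1) × subgroup share × ICC. That is 1.02 to 1.07 at a 2.5% share, so .419 becomes about .42 to .43. At a 10% share it is about 1.10 to 1.29, so .209 becomes about .22 to .24.
- **The power recalculation promised in Aim 2a** is tied to incidence rates from Component A. It does not address this figure.

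**Conclusion.** The concern holds. One MDES is given for two groups that need two. d=.20 is about right for 724 students (.21 with no covariate gain, .20 at a correlation of .28). For 181 students it is about .42 with no covariate gain and .36 at a correlation of .5, roughly twice the stated value, with 27% to 34% power at d=.20.

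These figures assume a two-sided .05 test, power .80, 1:1 allocation and independent students. The twofold ratio between the groups does not depend on the covariate assumption, and no plausible choice brings n=181 to .20.

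The importance is modest. Sample size, the primary analysis and every decision rule are untouched. The separate Mplus claim of power above .80 for b=.20 is not shown to be wrong. What needs correcting is the stated sensitivity for gender-minority students. It should be fixed.

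**What to change.** In SAP, Power Analyses, Aim 2b:

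1. Give each subgroup its own MDES on one common basis. With no covariate gain this is about d=.42 for n=181 and .21 for n=724. If .20 is kept for n=724, state the covariate correlation it needs (about .28) and give the n=181 value at that same correlation (about .40).
2. State sidedness, allocation and covariate correlation, and note that classroom clustering would normally raise both values.
3. Say whether the figures come from G-Power ANCOVA or from simulation, and confirm that the scale is d and not f.
4. For the Mplus result at b=.20, add the group split assumed and the scale of b.

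The cost is SAP wording only. One stated figure becomes less favourable; nothing in the design or analysis changes.
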